**(3) Study endpoint:**

**① Primary end point:** progression of DKD. Progression of DKD was defined as renal failure (requiring transplantation or dialysis, or persistent eGFR <15 ml/min/1.73 m^2) or a persistent decline of 30% in eGFR from baseline.

**② Secondary End Points:** I. Cardiogenic Death: Death caused by cardiac disease or related complications. II. Major Adverse Cardiovascular Events (MACE): Including myocardial infarction, stroke, unstable angina pectoris, and other significant cardiovascular events. III. Kidney Transplantation: Successful cases of kidney transplantation surgery. IV. Hypoglycemic Events: Documentation of the frequency and severity of hypoglycemia occurrences.

**(4) Specific objectives:** I. Evaluate the relationship between GV and prognosis in patients with DKD and determine the optimal GV control target. II. Screen for biomarkers of gut microbiota, metabolites, and inflammatory factors associated with DKD prognosis.

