## 5.4 Methods for Determining the Required Sample Size for Research

This exploratory study investigates the impact of gut microbiota and related metabolites on prognosis in diabetic kidney disease (DKD) patients. To achieve this, patients will be divided into two groups based on adverse prognosis outcomes, with subsequent comparisons of gut microbiota and metabolite differences between groups. To minimize microbial variations caused by individual differences, each group requires at least 30 participants, meaning there must be at least 30 patients with adverse prognosis events. Drawing from existing research, a 2023 study published in *\*Diabetes Care\** [Diabetes Care.2023;46(4):868-873.] included 975 DKD patients with an average follow-up of 4.7 years, reporting 156 major outcomes of DKD progression. Consequently, the total sample size was calculated as  $975/156*30=187.5$ . Considering potential dropouts and incomplete responses, we typically increase the sample size by 10%, ultimately enrolling 210 patients as the modeling cohort. Additionally, 60 DKD patients were included as a validation cohort. During actual recruitment, sample size adjustments may be made based on factors such as recruitment speed and data quality. Regular assessments of sample adequacy should also be conducted to ensure statistical power.

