#### **(5) Construction and Evaluation of Forecasting Model**

First, feature screening was performed using LASSO regression to select variables from five aspects: demographic characteristics, baseline scales, gut microbiota and non-target metabolites, and peripheral blood inflammatory biomarkers. Nine machine learning algorithms were employed to construct classification models, with performance evaluated through resampling training/verification mechanisms. The optimal model was selected via 10-fold cross-validation and performance metrics. Model performance and applicability were assessed using AUROC curves, calibration curves, Brier scores, and decision analysis plots. During training, validation, and testing phases of the optimal model, five-fold cross-validation and learning curves were used to evaluate model fit and stability. Finally, SHAP package was utilized to generate SHAP explanation plots to determine the importance and contribution of individual features.

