Based on baseline data, gut microbiota, serum metabolites, and inflammatory factors, predictive models will be constructed using machine learning algorithms (e.g., random forests, support vector machines, neural networks). Feature selection methods (e.g., LASSO regression, recursive feature elimination) will be employed to identify the most prognostic features, thereby enhancing model accuracy and interpretability. Internal stability of the models will be assessed through 10-fold cross-validation, while their generalization ability will be validated using independent validation cohorts.

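### LASSO or recursive elimination is said to identify the most prognostic features, but the planned checks test model performance, not whether the same features would be selected again

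*Protocol*

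**What the plan says.** Section 5.8.2 gives the selection step an inferential purpose: "Feature selection methods (e.g., LASSO regression, recursive feature elimination) will be employed to identify the most prognostic features". It adds that this will make the model more accurate and easier to interpret. Section 5.5(5) says that "feature screening was performed using LASSO regression to select variables from five aspects". Nine algorithms are then compared, and SHAP plots show how much each feature contributes to the chosen model.

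The checks attached to this step are:
- 10-fold cross-validation, which 5.8.2 describes as assessing the internal stability of the models and 5.5(5) uses to choose the best one;
- resampling, AUROC, calibration, Brier score and decision analysis (5.5(5));
- five-fold cross-validation with learning curves, for fit and stability of the chosen model (5.5(5));
- an independent validation cohort, for generalisation (5.8.2), of 60 patients (5.4).

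Marker identity is itself a planned result. Specific objective II in 3.1 reads: "Screen for biomarkers of gut microbiota, metabolites, and inflammatory factors associated with DKD prognosis". On size, 5.4 requires that "there must be at least 30 patients with adverse prognosis events".

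**The concern.** A LASSO penalty tuned to minimise prediction error does not limit how many irrelevant features are kept. Recursive elimination driven by performance does not either. With many correlated taxa and metabolites and few events, different feature sets can predict about equally well, and chance in the sample decides which is returned. A model can therefore pass every check listed in the protocol while its feature list would change in the next cohort. SHAP does not help here, because it ranks only the features that survived selection, within one fitted model.

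What is at stake is the identity of the reported markers, which is separate from optimism in the AUROC. A reader of the final report could not tell stable entries from accidental ones. Section 2.2.1 names personalised advice and earlier intervention as possible benefits of such markers.

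**Working it through.** **1. The plan's own sample size (5.4).** The source study "included 975 DKD patients with an average follow-up of 4.7 years, reporting 156 major outcomes of DKD progression", so the event proportion is 156/975 = 16.0%. The base size is "975/156*30=187.5". For dropout, "we typically increase the sample size by 10" per cent: 187.5 × 1.10 = 206.25 (207), or 187.5/0.90 = 208.3 (209). Both agree with the rounded figure: "ultimately enrolling 210 patients as the modeling cohort". The plan's number reproduces.

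**2. Events over the planned follow-up.** Section 5.5(3) sets follow-up at 3 years; the source proportion belongs to a mean of 4.7 years.
- At the source duration: 210 × 0.16 = 33.6 events.
- Three years, constant hazard: 210 × [1 − 0.84^(3/4.7)] = 210 × 0.1053 = 22.1.
- Three years, linear: 210 × 0.16 × 3/4.7 = 21.4.

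About 22 events are therefore expected before dropout, against a target of at least 30.

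**3. Stability of the selected set.** The protocol gives no number of candidate features, number of true markers, effect size, correlation or penalty rule, so all of these are assumptions. Pairs of independent cohorts of 210 were simulated. Each was analysed by logistic LASSO with the penalty at minimum deviance in 10-fold cross-validation. Within-block correlation was 0.3 unless stated.
- Not-true share = selected features that are not true markers / all selected features, pooled over cohorts.
- Overlap = features shared by both cohorts / features in either, pooled, by exact match.

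| Candidates | True markers | OR per SD | Events | Not true | Overlap |
|---|---|---|---|---|---|
| 100 | 10 | 1.5 | 30 | 70% | 12.8% |
| 200 | 10 | 1.5 | 30 | 76% | 7.3% |
| 200 | 5 | 2.0 | 30 | 78% | 13.1% |
| 200 | 40 | 1.3 | 30 | 41% | 19.9% |
| 500 | 10 | 1.5 | 30 | 83% | 1.5% |
| 500 (correlation 0) | 10 | 1.5 | 30 | 86% | 3.2% |
| 500 | 10 | 2.0 | 30 | 78% | 6.2% |
| 500 | 5 | 2.0 | 30 | 81% | 8.3% |
| 500 | 20 | 1.5 | 30 | 79% | 2.0% |
| 500 | 50 | 1.3 | 30 | 74% | 0.8% |
| 1000 | 10 | 1.5 | 30 | 87% | 0.6% |
| 500 | 10 | 1.5 | 22 | 86% | 1.7% |

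Each row rests on 24 pairs, so small differences mean little. With 60 pairs, the setting of 500 candidates, 10 markers and OR 1.5 gave 84% and 2.5% at 30 events, and 85% and 1.6% at 22. LASSO selected nothing in 31% of cohorts in both.

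At 30 events, 10 of the 11 settings lie between 70% and 87% not true. The exception, 41%, is the setting in which 40 of 200 candidates are true markers. A one-standard-error penalty, tried at 200 and 500 candidates (10 markers, OR 1.5, 30 events), gave 66% to 75% not true and 1% to 4% overlap.

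**4. Is low overlap only an effect of correlated stand-ins?** With 500 candidates in blocks of 10 (correlation 0.5), 10 true markers and OR 1.5, LASSO selected 13.5 features on average, of which 2.0 were true: (13.5 − 2.0)/13.5 = 85% not true. Crediting stand-ins, 8.1/13.5 = 60% still came from blocks with no true marker. Exact-match overlap was about 2%. Counting a match whenever both cohorts chose from the same block raised it to only 10% at 30 events and 4% at 22. With 200 candidates in the same layout, 36% came from blocks with no true marker, 78% were not true markers, and overlap was 5%.

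**The case against.** **Other routes to markers.** The study does not rely on LASSO alone. Section 5.5(4) compares prognostic groups to find markers, and 5.8.2 uses MaAsLin and OPLS-DA with adjustment. The LASSO sentence sits in the prediction-model paragraph, and 4.1.4 suggests that the model builds on factors already screened, so the candidate pool may be smaller than 500. This stands: the point is limited to the LASSO or elimination list and how it is described. A reader might infer that the whole biomarker objective fails, and the protocol does not support that. A smaller pool reduces the problem without removing it: at 100 candidates, 70% of selected features were still not true markers.

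**The study calls itself exploratory (5.4).** True, and candidate lists are expected to need replication. That is a reason to call the features candidates, whereas 5.8.2 says they are identified as the most prognostic.

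**This is detail for a SAP.** A separate SAP may exist and could specify selection frequencies, so their absence alone carries little weight. The point rests on what the protocol does state: the purpose given to the selection, and model cross-validation as the evidence of stability.

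**There are checks.** A reader might infer that nothing is checked. That would be wrong, since the protocol plans several sound checks of the model. The gap is specific to the selected set.

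**Conclusion.** The concern holds in a limited form. Sections 5.8.2 and 5.5(5) present the output of a prediction-tuned selector as identified prognostic features, and the stated checks do not test whether that output would recur. With 30 events targeted and about 22 expected over 3 years at the cited rate, the list is likely to be unstable.

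The size is a range under assumptions. For 100 to 1000 candidates, 5 to 50 true markers and odds ratios of 1.3 to 2.0, about 41% to 87% of selected features are not true markers (usually over 70%), and two cohorts share about 1% to 20% of them by exact match. It is tempting to quote a single pair of figures, such as 60% noise and 2% overlap, as a property of this design. The documents do not support that: the pair comes from one assumed setting, and its 60% counts only features from blocks with no true marker. The 22 events assume that the cited rate applies to this population and accrues at a roughly constant hazard. Prediction modelling can go ahead; it is the marker claim that needs changing.

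**What to change.** In 5.8.2 and 5.5(5):
1. Repeat the whole selection step, including penalty tuning, on 100 or more resamples of the modelling cohort, stratified by event.
2. Report each feature's selection frequency beside its SHAP rank.
3. Describe the selected features as candidate predictors or model inputs, and not as identified prognostic markers.
4. If stronger wording is wanted for some features, have the sponsor set the frequency cut-off before outcome data are analysed.

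No particular cut-off is prescribed, because a strict one has its own price. In the block setting with 500 candidates and 30 events, naming only features chosen in at least 60% of half-samples left 0.4 features per study, of which 0.17 were false (0.17/0.4, about 42%). That estimate comes from only 30 simulated data sets.

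The change needs no extra patients, visits or assays. It costs computing time, a few sentences and a more modest marker claim.

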## VI. Ethical Review and Informed Consent

### 6.1 Ethical Committee Review

This protocol, the written informed consent form, and all materials directly pertaining to the participants must be submitted to the ethics committee.

The study may commence only after obtaining written approval from the ethics committee. Investigators must submit an annual research report to the ethics committee at least once per year. When the study is suspended or completed, investigators must notify the ethics committee in writing. All changes during the study (including revisions to the protocol and/or informed consent forms) must be promptly reported to the ethics committee. No such changes may be implemented without prior ethics committee approval, except for those aimed at eliminating obvious and direct risks to participants. In such cases, the ethics committee will be notified.

## **6.2 Patient Information and Informed Consent**

Researchers must provide participants or their legal representatives with an easily understandable, ethics committee-approved informed consent form, and allow sufficient time for participants or their legal representatives to consider the study. Participants shall not be enrolled until they have obtained a signed written informed consent. Throughout the study period, all updated versions of the informed consent form and written information will be provided to participants. The informed consent form must be retained as an important document for clinical research review.

# **7. Quality Management Plan**

## **7.1 Measures to Improve the Consistency of Observations**

- (1) The participating clinical trial institutions are accredited medical device clinical trial facilities, with facilities and conditions meeting the requirements for safe and effective clinical trials. The research department's staffing and equipment meet the trial requirements, and the participating researchers possess the professional knowledge and experience required for the trial medical devices.
- (2) The variable factors should be strictly controlled in outpatient cases.
- (3) Through the training before clinical trial, the researchers have a full understanding of the clinical trial program and the specific connotation of each index, so as to improve the internal observation consistency and observer consistency of the clinical research data collector, and ensure the reliability of the clinical research conclusion.
- (4) The description of subjective symptoms should be objective and not suggestive or inducing; the objective indicators should be checked at the specified time and by the specified method.
- (5) Data that deviate significantly from the acceptable range must be verified and the researcher must provide a necessary explanation.
- (6) The evaluation of the questionnaire should be made by at least one attending physician and one physician independently. The person who filled in the clinical case report form should have the title of physician or above.

(7) Each clinical research unit should designate a person to check the progress of the clinical trial regularly and verify the data and records carefully.

**7.2 Measures to ensure subject compliance** should strictly control the variable factors of the subject from the following aspects:

- (1) Doctors participating in clinical trials are fixed;
- (2) The researcher should explain the process of the study and the obligations of the participants to the participants patiently, so that the participants can cooperate with the study.
- (3) The reasons for not meeting the diagnostic criteria should be recorded in detail.

**7.3 Researchers Should Follow the Requirements for Case Report Form Completion**

All observations and findings in the clinical trial should be verified to ensure the reliability of the data and that the conclusions are derived from the original data. Appropriate data management measures should be implemented during both the clinical trial and data processing phases.

**8. Confidentiality Measures**

We ensure the confidentiality of participants' identities and have established strict information security protocols to protect their privacy. (1) During data collection, personal identification information will be processed to safeguard participant privacy: Each participant's name will be assigned a unique identification number. Personal data and case records will be entered and stored by designated sample management personnel. Users will only see the identification number, with no access to personal names or other identifying details. (2) Participant information will be strictly confidential unless required by law. Sample data will be electronically stored in secure systems with password protection, accessible only to authorized personnel. Medical records will be kept at the hospital for researchers' review only. Government agencies, hospital ethics committees, and other relevant researchers may access participant data as required. (3) Research outcomes: Results may be published in medical journals in statistical analysis format, excluding any identifiable participant information and without commercial implications.

**9. Expected Progress and Completion Date of the Research Project**

Total duration of the project implementation	4 years
--	---------

Annual Plan Arrangements	
Schedule	Key contents and outcomes of the stage objectives
July 2025-May 2026	
Main content of the stage goal:
 
① Patient recruitment and enrollment  (2025.7-2025.12): Eligible subjects were recruited according to the inclusion and exclusion criteria in the protocol and enrolled.
 
② Glucose monitoring and sample collection  (2025.7-2025.12): CGM monitoring was performed for 14 days in enrolled patients, and stool and blood samples were collected. Ensure that the collection, preservation, and transportation of samples met relevant standards and requirements to provide high-quality samples for subsequent analysis.
 
③ Preliminary data analysis (2026.1-2026.5): The collected CGM data were preliminarily analyzed, patients were divided into different groups according to blood glucose variability, and preliminary data analysis report was completed.
 
④ Follow-up Initiation (2026.1-2026.5): A follow-up protocol and team were established to conduct a 3-year observation period for participants. Regular collection of clinical data—including diabetic kidney disease (DKD) progression, major adverse cardiac events (MACE), quality of life assessments, and complication occurrences—provided essential follow-up data for subsequent predictive model development. The follow-up program was successfully initiated and implemented.
 
⑤ Additional patient recruitment  (2026.1-2026.5): Start additional recruitment of patients in a validation cohort for validation of the prediction model.
 
Achievement
 
 
① The recruitment of patients was completed, and the enrollment rate reached the target.
 
② The collection rate of samples was 100%.
 
③ The preliminary data analysis report was completed.
 
④ The follow-up program was initiated and proceeded smoothly.
 
⑤ additional patients were recruited and the enrollment rate was as planned.
 

June 2026-December 2027	
Main content of the stage goal:
 
① Sequencing and Metabolic Analysis: 16S rRNA high-throughput sequencing was performed on collected fecal samples, while serum non-targeted LC-MS analysis was conducted on blood samples to obtain data on gut microbiota and serum metabolites. Bioinformatics methods were employed to analyze sequencing data, identifying the composition and functional characteristics of gut microbiota. Statistical analysis of metabolite data was performed to screen differential metabolites associated with glycemic variability. The final reports were compiled based on both sequencing and metabolic analysis results.
 
② Follow-up data collection: Continue to conduct patient follow-up to ensure the completeness and accuracy of the data. Organize and clean the collected follow-up data to establish a database, providing high-quality data support for subsequent predictive model construction.

	
The data integrity rate was over 95%.
 
③ Preliminary data analysis: The collected CGM data were preliminarily analyzed, patients were divided into different groups according to blood glucose variability, and preliminary data analysis report was completed.
 
④ Additional patient follow-up: The additional recruited patients were followed up for 3 years, and the clinical data of patients, including disease progression, occurrence of MACE, quality of life assessment, and occurrence of complications, were collected to provide data support for the validation of the prediction model. The complete rate of follow-up data was more than 95%.
 
Achievement
 
 
① The 16S rRNA sequencing and non-target metabolic analysis were completed.
 
② The complete rate of follow-up data was over 95%.
 
③ The preliminary data analysis report was completed.
 
④ The complete rate of follow-up data in the verification queue was over 95%.
 

January 2028-December 2028	
Main content of the stage goal:
 
① Follow-up Data Organization and Analysis: Conduct comprehensive final organization and analysis of collected follow-up data to ensure data integrity and accuracy. Perform statistical analysis to evaluate patient outcomes, including disease progression, major adverse cardiac events (MACE), quality of life assessment, and complication occurrence. Complete the follow-up data analysis report.
 
② Association Analysis: By integrating glycemic variability grouping results, this study investigates the relationship between gut microbiota characteristics and serum metabolite profiles with clinical outcomes, including disease progression, major adverse cardiovascular events (MACE), quality of life, short-term complications, and overall prognosis. Through correlation analysis and multiple regression analysis, we aim to uncover underlying biological mechanisms and predictive biomarkers, ultimately producing a comprehensive association analysis report.
 
③ Prediction Model Development: By integrating multi-dimensional data including baseline information, gut microbiota profiles, serum metabolite profiles, and inflammatory factors, we constructed predictive models using machine learning algorithms such as random forests, support vector machines, and neural networks. Through cross-validation and other optimization methods, we enhanced the model's predictive performance and stability, completing the initial development of the prediction model.
 
④ Model evaluation and validation: Appropriate evaluation metrics were used to assess the constructed prediction model, verifying its generalization capability and predictive performance across different datasets. Based on the evaluation results, the model was further optimized and adjusted to ensure reliability and practicality, and the model evaluation report was completed.
 
Achievement :
 
 
① The follow up data analysis report was completed.
 
② Complete the association analysis report.
 
③ The preliminary construction of the prediction model was completed.
 
④ The model evaluation report was completed.
 

January 2029-July 2029	
Main content of the stage goal:
 
① Clinical Validation of the Model: Validate the predictive model using additional recruited patients to evaluate its practical value and feasibility in real-world clinical settings. Based on validation results, make necessary adjustments and improvements to the model. This will facilitate its clinical application and promote its adoption, providing scientific evidence for prognostic assessment and personalized treatment of diabetic kidney disease (DKD) patients. The process will culminate in the completion of a clinical validation report.
 
② Complete the project: write the paper and complete the project report. Results:
 
 
① The clinical validation report was completed.
 
② The final report was completed, and the relevant academic papers were written and published.
 

------------------------	--

